### **7.2.5 Discharge**

The participant should only be discharged from the site after the minimum monitoring period and when judged stable in the opinion of Investigator/designee. Blood pressure and pulse rate will be taken prior to discharge from the site.

### **7.2.6 Documentation of investigational medicinal product administration**

The duration of the investigational medicinal product infusion will be recorded and calculated as follows:

- **Duration of infusion:** the amount of time elapsed from the infusion start time to the infusion stop time. Infusion start time is defined as the time point where investigational medicinal product is first infused into the participant. Infusion stop time is defined as the time point where the infusion pump completes infusion of the investigational medicinal product, not including the saline flush.

For example: an infusion with a start time of 12:00 PM would have a duration of infusion recorded as 30 minutes (a time between 12:00 PM and 12:30 PM).

The start time of IMP infusion, end time of IMP infusion, and the end time of saline flush should be documented accurately in source document.

## **7.3 Labelling**

Labels will be prepared in accordance with Good Manufacturing Practice (GMP) and local regulatory guidelines. The labels will fulfil GMP Annex 13 requirements for labelling. Label text will be translated into local language.

## **7.4 Storage**

All study interventions should be kept in a secure place under appropriate storage conditions. The investigational medicinal product should be stored at 2 to 8°C (36 to 46°F) and must not be frozen.

## **7.5 Compliance**

The administration of all study interventions (including investigational medicinal products) should be recorded in the appropriate sections of the Case Report Form. The investigational medicinal product will be administered by qualified study site personnel, who will monitor compliance.

## 7.6 Accountability

The study intervention provided for this study will be used only as directed in the study protocol.

The study site personnel will account for all study interventions dispensed to and returned from the participant.

Investigator or pharmacist is required to maintain accurate investigational medicinal product accountability records. Upon completion of the study, copies of investigational medicinal product accountability records will be returned to AstraZeneca or designee. Each administration of IV study therapy will be documented in the eCRF.

The unblinded AstraZeneca representative can perform complete IV study therapy accountability during each unblinded monitoring visit, including verifying documentation of drug receipt, dispensing, return, and destruction of IV study therapy and consistency of this documentation with physical inventory and IVRS/IWRS.

All unused investigational medicinal product will be returned to an AstraZeneca or designee-authorized depot or disposed of upon authorisation by AstraZeneca or designee or other written instructions provided by AstraZeneca or designee (for contact information and specific shipping instructions). Investigator or pharmacist should sign certificates of delivery and return.

Details regarding supplies, dose preparation, process for reporting product complaints, and accountability for the investigational medicinal product will be provided to the sites.

## 7.7 Concomitant and other treatments

Participants must be instructed not to take any medications, including over-the-counter products, without first consulting Investigator.

### 7.7.1 Prohibited/restricted medications

#### 7.7.1.1 Excluded medications: pre-study

Any medication listed in [Appendix I](#) must be discontinued prior to signing of the ICF.

#### 7.7.1.2 Excluded medications: during double-blind treatment period

Medications leading to immediate discontinuation of investigational medicinal product.

- Cyclophosphamide
- Biologic immunomodulators (e.g., belimumab, rituximab)
- JAK inhibitors (e.g., tofacitinib, baricitinib)

- BTK inhibitors (e.g., ibrutinib, acalabrutinib, zanubrutinib)
- Plasmapheresis
- Any immunoglobulin therapy
- IFN therapy (alpha 2a and 2b, beta 1a and 1b, and pegylated IFNs alpha 2a and 2b)
- Investigational agents
- Live or attenuated vaccines (e.g., BCG, herpes zoster, yellow fever); the Sponsor recommends that Investigators ensure all participants are up to date with required vaccinations prior to entry into the study
- Any medication listed in [Appendix I](#), except restrictions (e.g., sulfasalazine, danazol, and dapsone restrictions) as listed below in Section [7.7.1.3](#).
- Intravenous corticosteroids > 1 g methylprednisolone or equivalent

If any of the prohibited medications listed in [Appendix I](#) are used, except restricted drug listed below in Section [7.7.1.3](#), IMP must be immediately discontinued and participant will be regarded as non-responder for efficacy endpoints. Additional details are given in the SAP.

#### **7.7.1.3 Restricted medications during double-blind treatment period**

As anifrolumab is an investigative immunomodulatory agent, non-protocol permitted changes to immune modifiers or immunosuppressants on study are not permitted unless necessary to treat an adverse event or increased disease activity.

If a participant receives any of the following during study treatment period **the study physician must be notified immediately**. Sponsor will determine if the participant may continue to receive investigational medicinal product. Details on handling the analysis of data from participants who may use restricted medications are described in the SAP.

- 1 Sulfasalazine
- 2 Danazol, GnRH agonists or GnRH antagonists
- 3 Dapsone
- 4 Azathioprine > 200 mg/day or at a daily dose greater than that at Week 0 (Day 1)
- 5 Mycophenolate mofetil > 2.0 g/day or mycophenolic acid > 1.44 g/day or at a daily dose greater than that at Week 0 (Day 1)
- 6 Oral, SC, or intramuscular methotrexate > 25 mg/week or at a daily dose greater than that at Week 0 (Day 1)
- 7 Mizoribine > 150 mg/day or at a daily dose greater than that at Week 0 (Day 1)
- 8 Any change in route of administration of oral, SC, or intramuscular methotrexate
- 9 Intravenous corticosteroids > 40 mg/day but ≤ 1 g/day methylprednisolone or equivalent
- 10 Intramuscular corticosteroids > 80 mg/day methylprednisolone or equivalent

- 11 Subcutaneous or intramuscular corticosteroid precursors
- 12 Treatment with OCS > 40 mg/day prednisone or equivalent
- 13 Treatment with OCS above Day 1 dose for a dosing period > 14 days
- 14 Corticosteroids with a long biologic half-life (e.g., dexamethasone, betamethasone)
- 15 Tacrolimus (including topical) or cyclosporine, at a daily dose greater than that at Week 0 (Day 1)
- 16 Other immunosuppressants including but not limited to leflunomide.

Note: Cyclosporine eye drops are acceptable for use in the study. Topical tacrolimus is only acceptable if it's initiated **before** study and on stable regimen during study.

#### **7.7.1.4 Other concomitant treatment**

Other medication other than that described above, which is considered necessary for the participant's safety and well-being, may be given at the discretion of Investigator and recorded in the appropriate sections of the Case Report Form.

#### Inhaled corticosteroids:

Use of inhaled corticosteroids is allowed as needed for management of asthma or COPD.

#### Vitamins and herbal products:

Use of naturopathic, herbal or ayurvedic products should be avoided and participants should not start treatment with any of these or of nutritional/dietary supplements, vitamins, and/or minerals without discussing with Investigator.

#### Medicinal cannabinoid use:

Any new medicinal cannabinoid should not be started during the course of the study. Participants who are already on a stable regimen 8 weeks prior to screening may continue their regimen at the same stable dose through the course of study. Increases in strength or frequency is not allowed. Decrease or discontinuation is allowed for safety reasons.

### **7.7.2 Systemic Lupus Erythematosus therapy during double-blind treatment period**

Permitted medications for SOC SLE are described below. Concomitant medications should only be administered after all visit assessments, including investigational medicinal product administration and post-infusion PK blood draws (if applicable), with the exception of a participant with a previous infusion-related reaction who is to receive acetaminophen (paracetamol) or equivalent. The acetaminophen or equivalent should be given after all visit assessments other than the infusion have been completed, and prior to starting the infusion.

**Table 7 Permitted medications for SOC SLE**

Permitted SOC SLE	Limitations of Use
OCS	
 
Oral prednisone or equivalent up to <math>\leq 40</math> mg/day is permitted from at least 2 weeks prior to signing of the informed consent. The dose of oral prednisone must remain stable at least 2 weeks prior to Randomisation.
 
Where prednisone is the single SOC medication [i.e., the participant is not concurrently receiving any medications listed in Section 3.1 #7], a dose of oral prednisone <math>\geq 7.5</math> mg/day but <math>\leq 40</math> mg/day (or prednisone equivalent) for a minimum of 8 weeks prior to Randomisation is required.
 

Intramuscular corticosteroids	
 
Participants with increased SLE disease activity may receive 1 intramuscular injection of corticosteroids (methylprednisolone <math>\leq 80</math> mg or equivalent) instead of a burst and taper of OCS described above between Day 1 and Week 12.
 
May only be administered after all assessments and investigational medicinal product infusion have been completed at the visit.
 

Corticosteroid bursts and tapers	
 
Participants with increased SLE disease activity may receive 1 permitted burst and taper of corticosteroids between Day 1 and Week 12. Additional details on burst and taper for SLE and non-SLE (e.g., asthma or COPD exacerbation) disease activity are provided in Sections 7.7.1.4 to 7.7.3.
 

Intra-articular/tendon sheath/bursal corticosteroid injections	
 
Intra-articular/tendon sheath/bursal injection should be minimised. Participants may receive a maximum of 2 injections (for a total dose of <math>\leq 80</math> mg methylprednisolone or equivalent) instead of a burst and taper of OCS described above, between Day 1 and Week 12.
 
An intra-articular/tendon sheath/bursal injection may be allowed for non-SLE related disorders up to Week 40 if the symptoms of the disorder do not interfere with the ability to assess SLE-related endpoints. Investigator must contact the AstraZeneca study physician for permission to administer an intra-articular/tendon sheath/bursal corticosteroid injection prior to administration of corticosteroids for non-SLE related disorders.
 
If permission is given, the injection should not be administered until after the completion of all assessments, including investigational medicinal product administration and post-infusion PK blood draw (if applicable).
 

Antimalarials and immunosuppressants (azathioprine, methotrexate, and mycophenolate mofetil/mycophenolic acid, and mizoribine)	
 
Antimalarials and immunosuppressants (azathioprine, methotrexate, mycophenolate mofetil/mycophenolic acid, and mizoribine) are permitted, and at least 1 is required, as part of SLE therapy on Day 1 if the participant is not on OCS.
 
Dose regimens must remain stable from Day 1 to the completion of Week 52 but may be decreased for toxicity or to optimise management of an AE, such as infection. The toxicity/event must be confirmed as a documented AE. The dose can be returned to the Day 1 level if the toxicity/event resolves and if clinically indicated.
 
Antimalarials/immunosuppressants should not be changed if a participant has increased SLE disease activity during the OCS tapering period.
 

Nonsteroidal anti-inflammatory drugs (NSAIDs)	
 
• Prescription NSAIDs must remain stable from screening through Week 52 but can be reduced for reasons of toxicity but not efficacy. Prescription NSAIDs cannot be administered with other NSAIDs (including over-the-counter non-steroidals) except for low-dose aspirin.
 
• On a given visit day, prescription or non-prescription NSAIDs should not be taken until after all assessments have been completed.
 
• NSAIDs for analgesic purposes that never exceed label-approved doses of NSAIDs may be used for pain as required, based on Investigator judgment for up to 1 week at a time
 

Acetaminophen, paracetamol or equivalent	
 
• Pain medications should not be used within a minimum of 6 to 12 hours (based on known duration of effect) of a scheduled visit.
 
• Normal release (not extended release) acetaminophen or equivalent (e.g., paracetamol) may be used for pain as required.
 
• In a participant with a previous infusion-related reaction, acetaminophen or equivalent can be given after all visit assessments have been completed and prior to starting the infusion.
 

Low-dose aspirin	
 
• Low-dose aspirin (maximum of 325 mg/day) for cardiovascular disease is permitted.
 

Topical therapy	
 
• Concurrent use of topical therapy for cutaneous lupus erythematosus (e.g., corticosteroids) is permitted. Topical moisturisers are also permitted.
 
• Topical therapy must be the same being used at signing of the informed consent and the dose and frequency of application must be stable during screening.
 
• During the study, topical therapy may be reduced or discontinued based on clinical manifestations and Investigator discretion. Should cutaneous skin manifestations reoccur, the same topical therapy may be resumed up to the Day 1 dose.
 
• It is encouraged that no new dermatologic preparations be used for the duration of the study. It is also recommended that participants use sunscreen (list as concomitant medication for SLE) and avoid sun exposure during the study.
 

All permitted SOC SLE therapies received from initiation of screening through the end of the study will be recorded on the source document and CRF, and will include the specific indication for use (e.g., general SLE activity, skin involvement, nephritis, pleurisy) as well as the dose, start and stop dates, frequency, and route of administration. In addition, any change in permitted SOC SLE therapy and the reason for change must be documented.

If concurrent SOC medication requirements, e.g., glucocorticoids, immunosuppressants or anti-malarials, are not followed, participants may be considered as non-responders for efficacy endpoints. Additional details are given in the SAP.

### **7.7.3 Steroid use during the double-blind treatment period**

#### **7.7.3.1 Steroid burst and taper from Week 0 (Day 1) to Week 12**

In order to allow adequate time for the investigational medicinal product to achieve significant clinical benefit, Investigators may administer 1 burst and taper of corticosteroids between Week 0 (Day 1) and Week 12 for increased SLE disease activity/non-SLE causes.

A steroid burst as described below is defined as 1 of the following:

- OCS increase up to a maximum daily dose of 40 mg/day prednisone (or equivalent) for up to a total of 14 days and that must be fully administered and tapered to less than or equal to the Day 1 dose by the end of the 14th day. Any course of OCS above the Day 1 dose must not extend beyond Week 12, regardless of when the course was started;

OR

- Intramuscular methylprednisone ( $\leq 80$  mg) or equivalent administered as a single dose between Day 1 and Week 12;

OR

- A maximum of 2 intra-articular/tendon sheath/bursal injections (for a total methylprednisolone  $\leq 80$  mg or equivalent) can be given. Participants who receive any intra-articular/tendon sheath/bursal injections should not receive OCS or intramuscular burst between Day 1 and Week 12.

Participants who receive more than 1 steroid burst and taper from Week 0 (Day 1) to Week 12, or who violate any of the criteria above, may continue in the study, but may be considered as non-responders for efficacy endpoints (details are defined in the SAP), regardless of whether the OCS burst was administered for increased SLE activity or non-SLE causes.

#### **7.7.3.2 Increase in corticosteroids from Week 12 to Week 40**

Between Week 12 and Week 40, an increase in corticosteroid dose for increased SLE activity is not allowed. Participant receiving a steroid dose above their Week 0 (Day 1) dose may continue in the study, but may be considered as non-responders for efficacy endpoints (details are defined in the SAP).

An increase in OCS for non-SLE causes (e.g., asthma or COPD exacerbation) is allowed ONCE with AstraZeneca study physician approval between Week 12 and Week 40. This might include a non-SLE OCS up to  $\leq 20$  mg/day of prednisone (or equivalent) for up to a total of 14 days and must be fully administered and tapered to less than or equal to the Day 1 dose by the end of the 14th day and by the Week 40 visit day. This will be captured as burst and taper not attributable to SLE. The non-SLE indication must be clearly indicated in the source documents.

Participants who receive prednisone (or equivalent) for non-SLE indication at a total dose  $> 20$  mg/day but  $\leq 40$  mg/day for a dosing period of greater than 14 days may continue in the study, but may be considered as non-responders for efficacy endpoints (details are defined in the SAP). If a participant receives  $> 40$  mg prednisone or equivalent or a dose above baseline level for more than 14 days, it must be reported to the AstraZeneca study physician. The AstraZeneca study physician will determine if the participant may continue to receive investigational medicinal product.

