From Week 0 (after randomisation) to Week 12, participants may receive **only** 1 burst of corticosteroids for an increase in SLE disease activity or to control non-SLE related disease (e.g., asthma or chronic obstructive pulmonary disease [COPD] exacerbation).

An important secondary objective in the study is assessing whether anifrolumab improves the ability to reduce oral corticosteroid dose in participants to  $\leq 7.5$  mg prednisone or equivalent per day. For this reason, steroid tapering to a target OCS dose of  $\leq 7.5$  mg/day **must** be attempted in all participants with a baseline OCS dose  $\geq 10.0$  mg/day. This will commence at Week 8 and continue stepwise until the target dose is reached, unless at least 1 of the following criteria is met:

- SLEDAI-2K activity which is worsened compared to baseline in major organ systems (renal, CNS, cardiopulmonary, vasculitis, fever, thrombocytopenia, or haemolytic anaemia, or gastrointestinal activity)
- Newly affected organ system(s) based on the SLEDAI-2K, excluding serological abnormalities (dsDNA antibodies, hypocomplementemia)
- Moderate to severe skin disease as reflected by a Cutaneous Lupus Erythematosus Disease Area and Severity Index (CLASI) activity score of  $\geq 10$
- Extensive joint disease as reflected by  $\geq 8$  tender and  $\geq 8$  swollen joints

Although a recommended steroid-tapering regimen is provided, investigators will have flexibility in how the OCS dose is reduced at each visit. If steroid tapering is not attempted in an eligible participant, the Sponsor or Sponsor's designee **must** be contacted immediately.

Investigators will not be required, but may continue, to taper OCS dose beyond the target of 7.5 mg/day up to Week 40 based on disease activity. If a participant has an increase in disease activity secondary to OCS tapering, they may increase the dose up to a maximum of the

baseline OCS therapy dose from Week 8 up to Week 40. Participants who require OCS dose above their baseline level may continue in the study following consultation with the Sponsor or Sponsor's designee, but may be considered as non-responders for efficacy endpoints. **Steroid tapering will not be permitted after Week 40** (details are defined in the SAP).

Participants with OCS dose adjustment beyond the protocol-allowed threshold may be considered as non-responders for efficacy endpoints (details are defined in the Statistical Analysis Plan).

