#### 1.4.2 Protocol-specified steroid tapering

An important secondary objective in the study is assessing whether anifrolumab improves the ability to reduce oral corticosteroid dose in participants to  $\leq 7.5$  mg prednisone or equivalent per day. For this reason, steroid tapering to a target OCS dose of  $\leq 7.5$  mg/day **must** be attempted in all participants with a baseline OCS dose  $\geq 10.0$  mg/day. This will commence at Week 8 and continue stepwise until the target dose is reached, unless at least 1 of the following criteria is met:

- SLEDAI-2K activity which is worsened compared to baseline in major organ systems (renal, CNS, cardiopulmonary, vasculitis, fever, thrombocytopenia, or haemolytic anaemia, or gastrointestinal activity).
- Newly affected organ system(s) based on the SLEDAI-2K, excluding serological abnormalities (dsDNA antibodies, hypocomplementemia).
- Moderate to severe skin disease as reflected by a CLASI activity score of  $\geq 10$ .
- Extensive joint disease as reflected by  $\geq 8$  tender and  $\geq 8$  swollen joints.

Although a recommended steroid-tapering regimen is provided, Investigators will have flexibility in how the OCS dose is reduced at each visit. If steroid tapering is not attempted in an eligible participant, the Sponsor or Sponsor's designee **must** be contacted immediately.

Investigators will not be required, but may continue, to taper OCS dose beyond the target of 7.5 mg/day up to Week 40 based on disease activity. If a participant has an increase in disease activity secondary to OCS tapering, they may increase the dose up to a maximum of the baseline OCS therapy dose from Week 8 up to Week 40. Participants who require OCS dose above their baseline level may continue in the study following consultation with the Sponsor or Sponsor's designee, but may be considered as non-responders for efficacy endpoints. Steroid tapering will not be permitted after Week 40. Section 7.7.3 provides specific details on steroid use during the double-blind treatment period.

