#### **7.7.3.5 Protocol-specified steroid tapering Week 8 to Week 40**

All participants with a baseline prednisone (or equivalent) dose of  $\geq 10.0$  mg/day must attempt tapering of their dose to  $\leq 7.5$  mg/day. Tapering will start at Week 8 and continue through Week 40, unless there are signs of increased disease activity, including:

- SLEDAI-2K scores for renal, CNS, cardiopulmonary, vasculitis, fever, hemolytic anemia, thrombocytopenia or gastrointestinal activity; and/or
- SLEDAI-2K scores showing new activity in any organ system, except serological abnormalities (dsDNA, hypocomplementemia); and/or
- Moderate to severe skin disease as reflected by a Cutaneous Lupus Erythematosus Disease Area and Severity Index (CLASI) activity score of  $\geq 10$ ; and/or
- Extensive joint disease as reflected by  $\geq 8$  tender and  $\geq 8$  swollen joints

If steroid tapering is not attempted in an eligible participant, the Sponsor or Sponsor's designee must be contacted immediately. The recommended steroid-tapering regimen is provided in [Appendix N](#). However due to variability in participant responses to steroid

treatment and tolerability of taper, Investigators will have flexibility in how the OCS dose is reduced at each visit.

Investigators will not be required, but may continue, to taper OCS dose beyond the target of 7.5 mg/day up to Week 40 based on disease activity.

When available, if the lab values from the current visit at which tapering occurs, show increased SLE activity, the tapering can be reversed. If a participant has an increase in disease activity secondary to OCS tapering between Week 8 and Week 40, the OCS dose should be increased back to, but should not exceed, the Day 1 baseline dose. Participants who require OCS dose above their baseline level may continue in the study following consultation with the Sponsor or Sponsor's designee, but may be considered as non-responders for efficacy endpoints (details are defined in the SAP).

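### Section 7.7.3.2 bars any steroid increase for SLE activity in Weeks 12 to 40, while the synopsis and Sections 1.4.2 and 7.7.3.5 allow or direct a return up to the Day 1 dose; the passages need reconciling

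*Protocol*

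**What the plan says.** Four places in the protocol govern a steroid increase when SLE activity rises during the taper.

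- **Section 7.7.3.2:** "Between Week 12 and Week 40, an increase in corticosteroid dose for increased SLE activity is not allowed". The next sentence gives a consequence for a different threshold: "Participant receiving a steroid dose above their Week 0 (Day 1) dose may continue in the study", with possible non-responder status.
- **Section 1.4.2:** when activity rises because of the taper, "they may increase the dose up to a maximum of the baseline OCS therapy dose from Week 8 up to Week 40".
- **Synopsis, Study design:** the same permission, with the same cap and window.
- **Section 7.7.3.5:** in that situation "the OCS dose should be increased back to, but should not exceed, the Day 1 baseline dose". It also says: "When available, if the lab values from the current visit at which tapering occurs, show increased SLE activity, the tapering can be reversed".

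The rules on restricted medication use the Day 1 dose as reference. Item 13 of Section 7.7.1.3 reads "Treatment with OCS above Day 1 dose for a dosing period > 14 days". SAP Section 4.1.8.1 (intermittent events) and the worked example in SAP Appendix D, A 1.3, also look for a dose above Day 1 or baseline.

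The key secondary OCS endpoint (SAP Section 4.2.3.1) covers participants with baseline OCS of at least 10 mg/day. It requires 7.5 mg/day or less by Week 40, kept to Week 52. The taper must be attempted in these same participants unless one of the listed disease-activity exceptions applies.

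**The concern.** One clinical situation is forbidden an increase by one section, permitted it by two places and directed to it by a fourth. The prohibition carries no dose qualifier, no exception for regained taper steps and no pointer to Section 7.7.3.5.

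Three things depend on which section a site follows:

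- **Steroid exposure** between Week 12 and Week 40. Table 7 of the protocol tells sites not to change antimalarials or immunosuppressants for a rise in activity during the taper, so the steroid rule carries more weight at that moment.
- **The OCS endpoint**, through the dose at Week 40.
- **Deviation handling.** A site that complies with Section 7.7.3.5 can be recorded as deviating from Section 7.7.3.2, and the reverse. The text that follows Table 7 in Section 7.7.2 allows non-responder status when glucocorticoid requirements are not followed, and leaves the detail to the SAP.

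**Working it through.** The plan states no figure on this point, so the check is mainly a comparison of texts.

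**1. Windows.** The prohibition runs from Week 12 to Week 40. The permission and the direction run from Week 8 to Week 40. The overlap is 40 − 12 = 28 weeks, the whole of the prohibition's window.

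**2. Triggers.**

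| Place | Trigger | Instruction |
|---|---|---|
| 7.7.3.2 | Increased SLE activity, any cause | No increase |
| Synopsis; 1.4.2 | Activity rising because of the taper | *May* increase, up to baseline |
| 7.7.3.5 | Activity rising because of the taper | *Should* increase, up to Day 1 |
| 7.7.3.5 | Laboratory evidence of SLE activity at a taper visit | Taper step *can* be reversed |

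The taper triggers are narrower than the trigger in 7.7.3.2 and lie inside it. Read literally, then, every increase that the taper passages allow or direct in Weeks 12 to 40 is also barred by 7.7.3.2.

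**3. Does 7.7.3.2 limit itself to doses above Day 1?** Its first sentence does not. Its second sentence attaches an analysis consequence to doses above Day 1 but does not narrow the prohibition. Section 7.7.3.3, on the period after Week 40, is built in the same way and writes its exceptions out; 7.7.3.2 has none for SLE activity. For that later period, SAP Section 4.2.3.1 measures an increase against the dose at Week 40 + 1 day, not against Day 1. A site could reasonably read 7.7.3.2 as also meaning above the current dose.

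**4. Largest dose difference.** The formula is Day 1 dose minus tapered dose. It assumes that the taper has reached and stopped at the 7.5 mg/day target, and that one reading gives a full return to Day 1 and the other no increase.

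- Day 1 dose 20 mg/day: 20 − 7.5 = 12.5 mg/day
- Day 1 dose 40 mg/day (the eligibility maximum): 40 − 7.5 = 32.5 mg/day

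These are maxima under those assumptions. A partial taper or a partial return gives less.

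**5. Endpoint.** A participant returned to a Day 1 dose of 10 mg/day or more and still on it at Week 40 fails the criterion of 7.5 mg/day or less. The same participant held at 7.5 mg/day could meet it. A participant returned to Day 1 and tapered again to 7.5 mg/day or less by Week 40 does not fail on that account.

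**6. Restricted-medication status.** A return to Day 1, and no higher, does not meet item 13 or the visible SAP rules. The Appendix D rule tables are redacted and the review charter is not part of the documents.

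**The case against.** The strongest reply is that Section 7.7.3.2 is about bursts after Week 12 and means no SLE-driven dose above Day 1. It follows the burst section (7.7.3.1), it calls its own non-SLE allowance a burst and taper, and doses in 7.7.3 are repeatedly judged against Day 1. On that reading 7.7.3.5 is the specific taper rule with the same ceiling, and the two fit. This is plausible as the intent. It does not settle the matter, because the sentence that sites read does not say it, and the difference between *may* and *should* remains on either reading. That difference is modest: cap and window are the same, and Section 1.4.2 refers to Section 7.7.3 for detail.

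A reader might infer more than the documents support:

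- **That a known share of participants is affected.** No document says how many will have activity rising because of the taper in Weeks 12 to 40, and the taper itself has stated exceptions.
- **That a return to Day 1 makes a participant a non-responder.** The visible restricted-medication rules point the other way, and Section 7.7.2 says only that non-response may be considered.
- **That participants who need more steroid must leave the study.** Even those above Day 1 may continue.
- **That the treatment comparison is biased.** The trial is randomised and double-blind. Mixed site practice would mainly add noise, and nothing here shows a difference between arms.
- **That the charter or Appendix D is misaligned.** The relevant text cannot be seen.

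**Conclusion.** The conflict stands as a matter of wording. For 28 weeks, in the population of the key secondary OCS endpoint, Section 7.7.3.2 taken literally bars what the synopsis and Section 1.4.2 permit and Section 7.7.3.5 directs. Sites could manage the same participant differently, with effects on steroid exposure, on whether the OCS criterion is met and on what is recorded as a deviation. The dose difference is at most 12.5 or 32.5 mg/day for Day 1 doses of 20 or 40 mg/day, on the assumptions above. The frequency is unknown, and no effect on the primary Bayesian analysis is shown. This is an inconsistency worth correcting, not a flaw in the design. No view is taken on which clinical rule is right.

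**What to change.** Reconcile the synopsis and Sections 1.4.2, 7.7.3.2 and 7.7.3.5 into one statement on SLE-driven increases that stay at or below the Day 1 dose in Weeks 12 to 40. It should settle the difference between *may* and *should*, and say how the laboratory-based reversal fits. State it once and cross-refer to it from the other places. The sponsor decides which clinical rule applies.

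The sponsor should also confirm that the protocol deviation plan and the restricted-medication review follow that statement. SAP Section 3.3.5 has the list of important deviations finalised before database lock and unblinding, so one agreed reading is needed by then, even if many participants have already passed Week 40.

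The cost is a short protocol wording change or a clarification letter to sites, plus a check of the review documents. Sample size and the planned analyses are unchanged.
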